3.2 Clinical Evidence to Date

In a recent prospective pilot trial performed at our institution, 24 cases with unsuccessful treatment of positional functional posterior shoulder instability were enrolled in a new functional treatment concept involving electric muscle stimulation (EMS) therapy. In this negative-selection of patients, where previous treatment including conventional physiotherapy for at least three months with or without additional surgical stabilization attempts had failed, an improvement in subjective and objective outcome parameters was achieved and stability was reobtained in most patients within 3-6 weeks of treatment.

3.3 Rationale for the intended treatment

A continuous and iterative improvement process of the EMS treatment protocol under investigation was completed during the recently accomplished prospective pilot trial based on the patients' objective and subjective response as well as adherence to the prescribed therapy plan. The amount of physiotherapy session or EMS treatments is based on a typical amount of physiotherapy sessions a patient undergoes for treatment of shoulder instability.

3.4 Explanation for choice of comparator (or placebo)

Pathology-targeted physiotherapy is the current treatment standard of FPSI and will serve as the control intervention in the proposed trial. All involved centers specified and agreed on a standardized exercise protocol for the control intervention during a Delphi survey. The control intervention will have the same exercises, duration, intervals, and instructing physiotherapist (at each center) as the experimental intervention. An optional bi-directional cross-over into the other intervention group (experimental or control) is possible after follow-up examination at the time-point T2 (3 months after the beginning/6 weeks after the end of the intervention)

in the case of subjectively unsatisfying result despite completion of the originally assigned intervention.

3.5 Risks / Benefits

No adverse events were recorded in any of the 24 cases involved in the pilot trial (carried out at Charitè University Hospital, Berlin, Germany). In this pilot trial 24 cases with unsuccessful treatment of FPSI were enrolled in a new functional treatment concept involving electric muscle stimulation (EMS) therapy. In this negative-selection of patients where previous treatment including conventional physiotherapy for at least three months with or without additional surgical stabilization attempts had failed an improvement in subjective and objective outcome parameters could be achieved and stability was reobtained in most patients within 3-6 weeks of treatment.¹³

3.6 Justification of choice of study population

All patients with FPSI will be included in this study irrespective of age, gender, degree of hyperlaxity, or duration of symptoms. Exclusion criteria focus on structural anomalies (static posterior migration, connective tissue diseases, degenerative joint diseases, structural defects) and other pathologies (multidirectional instability, neurological disorder or nerve injuries, existing pain syndrome, medical contraindication to EMS treatment) hindering, impeding, or prohibiting the complete administration of the control or experimental intervention. Additionally, patients with previous participation in a pathology-targeted standardized EMS or physiotherapy protocol are excluded in order to avoid patient's potential unwillingness to participate in or preformed mindset towards an intervention that they previously tried already without success. This combination of inclusion and exclusion criteria seems adequate to create a homogeneous group of study participants that still represents the typical characteristics of the majority of patients suffering from FPSI.

4. STUDY OBJECTIVES

4.1 Overall Objective

If the null-hypothesis can be rejected and the results of the new therapy concept show more effectiveness than the current treatment standard a much needed step-forward in the treatment of patients with FPSI will be achieved and likely lead to a complete change in the current treatment paradigms for this challenging pathology.

4.2 **Primary Objective**

This study wants to show that a certain therapy for FPSI leads to a better WOSI Score.

4.3 Secondary Objectives

This study wants to show that a certain therapy with FPSI leads to a better SSV, ROM respectively higher "satisfaction level with the treatment" and strength (abduction, flexion, rotation). Also the other secondary objectives like "impairment of daily activities", "impairment of the job", "sports impairment" and pain level should be decreased after a FPSI therapy.

4.4 Safety Objectives

Not applicable.

5. STUDY OUTCOMES

5.1 **Primary Outcome**

For the examined pathology there is no guideline regarding recommended outcome measurements or core outcome sets. The Western Ontario Shoulder Instability Index (WOSI) which is a shoulder instability-specific subjective outcome measurement with proven high validity, reliability, and responsiveness¹⁰ recommended for the evaluation of shoulder instability¹⁵ will serve as main outcome measurement. The WOSI covers four categories: physical symptoms (10 items); sports, recreation, and work (4 items); lifestyle (4 items); and emotions (3 items). The reason to choose a subjective outcome measurement is the fact that 1) the patients' own perception of their shoulder function is a key factor to determine the success of treatment,¹⁶ 2) a comprehensive, valid, and reliable objective clinical or radiographic outcome measurement in this highly-dynamic pathology is not obtainable, and 3) objective clinical outcome measurements might slightly vary between participating centers despite standardization.

5.2 Secondary Outcomes

SSV: The Subjective Shoulder Value (SSV) is based on a single question that is answered subjectively the patients. The English formulation of this question is: "What is the overall percent value of your shoulder if a completely normal shoulder represents 100%?"¹

ROM

The following active and passive range of motion parameters will be documented:

Strength:

Abduction strength: The abduction strength (kg) is measured by 90° abduction in both shoulders (i.e. measured also for the opposite shoulder) using a spring balance (e.g. Pesola AG, Baar, Switzerland). The test is done with the patients standing. The arm should be abducted 90 degrees in scapula plane with the thumb showing upward. Only one measurement is performed.

Flexion strength: The flexion strength (kg) is measured by 90° flexion in both shoulders (i.e. measured also for the opposite shoulder) using a spring balance (e.g. Pesola AG, Baar, Switzerland). The test is done with the patients standing with thumb showing upward.

External rotation strength: The external rotation strength (kg) is measured with the arm in neutral rotation and the elbow flexed 90° in both shoulders (i.e. measured also for the opposite shoulder) using a spring balance (e.g. Pesola AG, Baar, Switzerland). The test is done with the patients standing with thumb showing upward.

Internal rotation strength: The internal rotation strength (kg) is measured with the arm in neutral rotation and the elbow flexed 90° in both shoulders (i.e. measured also for the opposite shoulder) using a spring balance (e.g. Pesola AG, Baar, Switzerland). The test is done with the patients standing with thumb showing upward.

Pain Level:

The pain level will be assessed with NRS (0 = no pain, 10 = worst pain).

Questions about impairment:

The patient will be asked about the impairment in daily activities, in the job and in sports activities (0% = no impairment, 100% = total restriction; 20% steps).

Satisfaction:

The patient will be asked about the level of satisfaction of the treatment (0% = not at all, 100% = complete satisfaction)

Characteristic of the subluxations

The patients will be asked about the subluxations events (e.g. first time, which movements) and previous treatments (e.g. surgery, physiotherapy).

5.3 Safety Outcomes

Based on the complication-free pilot trial, no adverse events are pre-specified but continuous recording of unexpected adverse events will be executed in both treatment arms. In the case that adverse events are recorded, the independent expert group and ethical committee supervising the trial will be informed and may decide whether the trial can be continued or must be stopped.

6. STUDY DESIGN

6.1 General study design and justification of design

This is a multicentric, prospective, randomized and optional crossover study.

There will be an intervention period of 6 weeks and afterwards a follow up time of totally 12 months. After 3 months the primary endpoint (WOSI) will be measured. Afterwards the mentioned optional cross-over in the other group is allowed in the case of subjectively unsatisfying result despite completion of the originally assigned intervention. This approach ensures that the primary endpoint still can be obtained and only secondary endpoints will be jeopardized if an unexpected high rate of cross-over from one intervention group to the other occurs.

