6.2 Methods of minimising bias

The strict inclusion and exclusion criteria create a homogeneous group of study participants. After a patient has decided to enter the study and provided written informed consent, he/she will be randomized in one of the two treatment groups (allocation ratio 1:1) (details: see 6.2.1).

The multicentric design will introduce variation in expertise of persons executing the interventions, however all interventions in all centers are completed based on pre-defined standardized protocols. We will also adjust the statistical analyses for clustering of patients within centers. Analysis will therefore include measured effect differences between centers.

Furthermore the multicentric design helps to diminish the risk of confirmation bias since the experimental intervention was developed by one of the participating trial centers where the experimental intervention is likely to unwittingly be favoured. This trial setting allows to objectively predict if the study results can be generally reproduced if the study protocols are applied in other institutions.

Since the main outcome measurement is a subjective score, blinding of the examiner is not necessary. Blinding of the patients themselves is not possible due to the nature of experimental and control intervention. This circumstance can potentially introduce a confirmation bias from the patients' side. However, according to the trial design, all patients with previous participation in a pathology-targeted standardized EMS or physiotherapy protocol are excluded which reduces the risk for a pre-conditioned mindset in patients.

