7.2 Recruitment and screening

The estimated prevalence of functional shoulder instability is approximately 0.05% of the population⁵. More precise numbers are not available in the literature. In our pilot trial we treated over 20 cases suffering from FPSI within a one-year timespan at our referral center for shoulder pathologies. All centers included in the proposed project have a similarly large access to potential study participants. Therefore, a sufficient access to the potential study population is available to make recruitment of the planned number of patients within the predefined time period likely. Moreover, the observed acceptance rate of the patients to

participate in a standardized training protocol both, with or without EMS, was very high in the pilot trial. Therefore, the willingness to participate in a randomized trial is expected to be substantial as well, especially considering the offered optional bi-directional cross-over design making both types of intervention accessible for the patients.

During the pilot trial many patients expressed the desire to make this new form of treatment available more close to their home which led us to the decision to turn the proposed project into a multicentric trial involving not only some of the largest shoulder centers in German speaking countries but also considering strategical geographical locations. This should help to reduce time-comsuming travel and costly hotel stays for the patients and their parents and thus facilitate recruitment.

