8.3 Crossover

An optional bi-directional cross-over into the other intervention group (experimental or control) is possible after follow-up examination at the time-point T2 (3 months after the beginning/6 weeks after the end of the intervention) in the case of subjectively unsatisfying result despite completion of the originally assigned intervention.

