11. QUALITY ASSURANCE AND CONTROL

11.1 Data handling and record keeping / archiving

11.1.1 Case Report Forms

Source data includes all information in original records, observations, or other activities necessary for the reconstruction and evaluation of the documentation process for this study. Samples of source data include, but are not limited to, medical history information, demographics, informed consent, patient identification number, questionnaire responses and outcome scores.

Source data are entered by the study staff, physicians and patients either on paper CRF / source worksheets (WS) or electronically into eCRFs web-based Electronic Data Capture system (REDCap)². Patients are invited to enter study questionnaires electronically, either on a tablet computer at the clinic or from home after invitation by email with an electronic link to the relevant eCRF. Alternatively they will complete paper-based CRFs.

In addition, selected patient demographics and surgical parameters may be imported into REDCap from the patient information system as requested by respective study sites.

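### The prospect of crossover, granted on self-reported dissatisfaction around the 3-month visit, may influence the unblinded, self-rated primary WOSI, and the protocol does not keep the two apart

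*Protocol*

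**What the plan says.** Section 6.1 gives the order of events: "After 3 months the primary endpoint (WOSI) will be measured. Afterwards the mentioned optional cross-over in the other group is allowed". It then draws the conclusion under review: "This approach ensures that the primary endpoint still can be obtained and only secondary endpoints will be jeopardized", should crossover turn out to be unexpectedly frequent.

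Section 8.3 contains the rule itself. A switch may go in either direction. Its timing is described as "possible after follow-up examination at the time-point T2 (3 months after the beginning/6 weeks after the end of the intervention", while the condition attached to it reads "in the case of subjectively unsatisfying result despite completion of the originally assigned intervention". No threshold is given, and no instrument is named on which dissatisfaction is to be recorded.

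Four other places bear on the point:
- Section 6.2 on blinding: "Blinding of the patients themselves is not possible due to the nature of experimental and control intervention". It accepts that this may bias patients' responses. The mitigation it offers is the exclusion of patients who have already been through a standardised programme of either kind.
- Section 7.2 counts on the offer to help recruitment, "especially considering the offered optional bi-directional cross-over design making both types of intervention accessible for the patients".
- Section 11.1.1 on data capture: "Patients are invited to enter study questionnaires electronically, either on a tablet computer at the clinic or from home after invitation by email".
- Sections 8.1 and 8.2 describe the arms. EMS is a set of targeted exercises with simultaneous stimulation. The control has the same exercises, duration, intervals and physiotherapist, without the stimulation.

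**The concern.** Section 6.1 considers one way in which crossover could harm the primary comparison: patients receiving the other treatment before the endpoint is measured. A second way is left out. A patient who knows that a switch is available, and that it depends on how satisfied he or she feels, rates the primary endpoint around the time the switch is decided. Someone hoping to switch has a reason to present the result as poor, and nothing tells that patient that the WOSI answers have no bearing on access.

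If this worked equally in both arms it would cancel in the difference. The design gives some reason to expect otherwise. A control patient who crosses over gains a component not yet tried, whereas an EMS patient who crosses over repeats the same exercises without stimulation. A larger downward shift in the control arm would be counted as benefit of EMS.

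**Working it through.** **The protocol's own figure.** Inputs from section 10.2: MCID 10.4, SD 13 (both in percentage points of the WOSI), power 80%, alpha 5%. Allocation is 1:1 (6.2).
- Effect size: d = 10.4 / 13 = 0.8.
- A two-sided, two-sample t test needs 25.5 per arm, rounded up to 26, so 52 in total. This matches the stated 52. Power at 26 per arm is 80.7%.

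**What the text fixes and what it leaves open.**

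| Step around the 3-month visit | Where | Fixed? |
|---|---|---|
| WOSI measured before the treatment switch | 6.1; 9.1 gives the same order | Yes |
| Switch only after the 3-month follow-up examination | 8.3 | Yes |
| Questionnaires belong to the follow-up visit | 9.2.3 | Yes |
| WOSI submitted before crossover is discussed or requested | none | No |
| Separate record of the crossover request | none | No |
| Patients told that the WOSI does not affect access | none in the text at hand (consent pages are not shown) | Open |

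So the order of WOSI and treatment is set. The order of WOSI and crossover conversation is not, and completion at home (11.1.1) allows the conversation to come first.

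**Size, on assumed inputs.** Suppose a share f of control patients rates the WOSI s points worse because a switch is on offer, and no EMS patient does. Neither f nor s can be taken from the protocol.
- Bias in the mean difference: b = f × s.
- Standard error: SE = 13 × √(2/26) = 3.61.
- With no true effect, the two-sided rejection rate is the power of the t test on 50 degrees of freedom at non-centrality b / SE.

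| f | s | b | b / MCID | b / SE | Two-sided false-positive rate |
|---|---|---|---|---|---|
| 0 | – | 0 | 0% | 0 | 5.0% |
| 25% | 5 | 1.25 | 12% | 0.35 | 6.3% |
| 25% | 10.4 | 2.6 | 25% | 0.72 | 10.9% |
| 50% | 10.4 | 5.2 | 50% | 1.44 | 29.3% |

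If EMS patients shift as well, b is the difference between the two arms' average shifts. It is zero when they are equal.

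**The case against.** The strongest defence is that 6.1 answers the question it asks. Its sentence concerns a high rate of actual switching, and against that the ordering does protect the 3-month WOSI. This stands. It depends on the endpoint falling 3 months after the start of treatment, as the synopsis and 8.3 have it. Section 9.1 instead places it 3 months after the intervention ends. That is a separate conflict, and those sections must be reconciled.

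A reader might infer more: that nothing makes the WOSI come first, so EMS sessions could be under way in a control patient before the 3-month WOSI is completed. The protocol does not support this. Section 6.1 has the WOSI measured and the switch allowed only afterwards, and 9.2.3 makes the questionnaires part of the follow-up visit. Treatment before the rating would be a protocol deviation.

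It can also be said that no section ties crossover to the WOSI. Satisfaction with treatment is a separate item (5.2), and a patient can ask to switch without lowering any WOSI answer. That is correct, and it is why the concern is one of influence rather than of a rule that rewards a low score. But patients are nowhere told so in the text at hand.

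Crossover also runs both ways, and 7.2 reports very good acceptance of training with and without EMS in the pilot. The one-sided incentive is therefore inferred from the make-up of the two arms and has not been observed.

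Finally, patients know of the option from enrolment, so locking the questionnaire cannot remove anticipation. This also stands, and it limits what the fix can achieve.

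**Conclusion.** The point holds as a modest, cheaply reduced risk of bias in the primary endpoint. An unblinded patient rates the WOSI around the same visit at which crossover is granted on self-reported dissatisfaction, and the protocol does not separate the two. The claim in 6.1 that secondary endpoints alone are at risk is sound for contamination by switching and too broad for anticipation.

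The likely direction, if there is a net effect, favours EMS, because control patients have more to gain from a switch. That is plausible but not shown.

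The size is unknown. The range of about 6% to 29% for the false-positive rate rests wholly on assumed shares and shifts, with the EMS arm assumed not to shift. The mildest case barely moves the error rate. The largest needs half the control arm to shift by a full MCID.

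**What to change.** - **Sections 8.3 and 9.2.3:** require the 3-month WOSI to be submitted and locked in REDCap before crossover is discussed or requested. Record the request on a separate form.
- **Protocol and patient information:** state that WOSI answers are neither seen nor used when crossover is decided. Of the changes, this one acts most directly on the incentive.
- **Section 6.1:** limit the claim about secondary endpoints to contamination by actual switching, and add that anticipation of crossover may still influence the self-rated primary endpoint.

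The condition for crossover does not change. The cost is protocol wording, one REDCap form with a branching rule, and a brief wait for a patient who has not yet submitted the questionnaire. Anticipation is reduced, not removed, so the limitation should also be acknowledged when the result is reported.

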6.2 Methods of minimising bias

The strict inclusion and exclusion criteria create a homogeneous group of study participants. After a patient has decided to enter the study and provided written informed consent, he/she will be randomized in one of the two treatment groups (allocation ratio 1:1) (details: see 6.2.1).

The multicentric design will introduce variation in expertise of persons executing the interventions, however all interventions in all centers are completed based on pre-defined standardized protocols. We will also adjust the statistical analyses for clustering of patients within centers. Analysis will therefore include measured effect differences between centers.

Furthermore the multicentric design helps to diminish the risk of confirmation bias since the experimental intervention was developed by one of the participating trial centers where the experimental intervention is likely to unwittingly be favoured. This trial setting allows to objectively predict if the study results can be generally reproduced if the study protocols are applied in other institutions.

Since the main outcome measurement is a subjective score, blinding of the examiner is not necessary. Blinding of the patients themselves is not possible due to the nature of experimental and control intervention. This circumstance can potentially introduce a confirmation bias from the patients' side. However, according to the trial design, all patients with previous participation in a pathology-targeted standardized EMS or physiotherapy protocol are excluded which reduces the risk for a pre-conditioned mindset in patients.

6.2.1 Randomisation

A randomization sequence will be generated electronically using Stata (StataCorp LP, Texas USA) separately for each participating centers for up to X patients and loaded within an online study database in REDCap² (Research Electronic Data Capture) for automatic concealed allocation. Block-randomization with blocks of 2 and 4 will be used to minimize the risk of unequal group sizes. The randomization process allows to divide the study participants into two cohorts of comparable characteristics. We will compare these cohorts with regards to potential confounding factors before the outcome analyses and adjust statistically for any observed imbalance as appropriate.

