8. STUDY INTERVENTION

8.1 Experimental Intervention (treatment)

The experimental intervention consists of pathology-targeted physiotherapy exercises with simultaneous EMS stimulation which was developed and tested in a pilot trial involving patients without previous treatment success. Electric stimulation targets the external rotators and scapula retractors and consists of rectangular symmetrically compensated alternate current with a frequency of 30Hz and varying intensity. The training involves a combination of pre-defined pathology-targeted exercises with increasing difficulty and intensity. The intervention will include 18 one-hour trainings evenly distributed over a time period of 6 weeks and will be administered by the same physiotherapist at each participating center based on a standardized protocol.

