8.2 Control Intervention (standard therapy)

The control intervention consists of the current treatment standard for FPSI, namely pathology-targeted physiotherapy with exercises that were further specified during a Delphi survey. The control intervention will have the same exercises, duration, intervals, and instructing physiotherapist (at each center) as the experimental intervention.

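### Centre-specific blocks of 2 and 4, with sizes printed in the protocol of an open trial, seriously weaken allocation concealment

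*Protocol*

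**What the plan says.** Protocol section 6.2.1 (Randomisation) has the sequence generated "separately for each participating centers for up to X patients" and loaded into REDCap "for automatic concealed allocation". It then fixes the block sizes and gives the reason: "Block-randomization with blocks of 2 and 4 will be used to minimize the risk of unequal group sizes". The proportions in which the two sizes are mixed are not stated.

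The trial is open. Section 6.2 (Methods of minimising bias) says: "Blinding of the patients themselves is not possible due to the nature of experimental and control intervention". It adds that, because the main outcome is a subjective score, "blinding of the examiner is not necessary". Section 8.1 says that the experimental training "will be administered by the same physiotherapist at each participating center", and section 8.2 gives the control arm the same instructor: "The control intervention will have the same exercises, duration, intervals, and instructing physiotherapist (at each center) as the experimental intervention".

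Section 6.2 also concedes that the centre that developed the experimental treatment may favour it without meaning to. Sections 6.2.1, 10.3.1 and 10.3.2 plan a baseline comparison and adjustment for observed imbalance. The protocol names no measure against prediction of the next allocation, such as larger blocks or sizes withheld from sites.

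**The concern.** Concealment has two parts: nobody can look up the next entry, and nobody can work it out. REDCap secures the first. The second depends on the block sizes, on who knows them, and on whether past allocations are visible. Here the blocks are the smallest possible, the sizes are published to sites, each centre has its own short list, and the arms are open.

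A recruiter who can foresee the arm can delay, encourage or discourage a patient before consent. Some entry criteria leave room for judgement, for example pain that interferes with training, or inability to follow study procedures (section 7.1). Patients also have at least 24 hours to decide (section 2.4), so timing is flexible. Differences introduced in this way fall on prognosis at entry, and a patient-reported WOSI gives no protection against them. Adjustment for measured baseline factors cannot remove unmeasured differences such as motivation or expectation. With 52 evaluable patients planned, a few steered enrolments could matter.

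**Working it through.** **Inputs.** Block sizes 2 and 4, separate lists by centre (section 6.2.1); 1:1 allocation (section 6.2); six centres (synopsis); 66 patients to be assigned (section 10.2). The protocol gives no figure for predictability, so there is none to reproduce. The 66 is consistent with its own steps: 52/0.80 = 65, taken up to the even number 66, and 66/0.75 = 88 to be assessed. An even spread gives 66/6 = 11 per centre. The synopsis calls 88 the number included; 88/6 = 14.7, so 15 per centre is used as a sensitivity case.

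**Assumptions.** Sizes 2 and 4 are equally likely. The observer knows the sizes and all earlier allocations at the centre, but not where blocks begin.

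**First patients at a centre.**
- Patient 1: 50/50.
- Patient 2 is opposite to patient 1 with probability ½ × 1 + ½ × 2/3 = 5/6 = 83.3%.
- If patients 1 and 2 are alike (probability 1/6), the block must be of size 4, and patients 3 and 4 are both certain.
- If they differ (5/6), the block is of size 4 with probability (½ × 2/3)/(5/6) = 0.4. Patient 3 is then 50/50. Patient 4 is opposite to patient 3 with probability 0.4 × 1 + 0.6 × 5/6 = 90%.

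**Exact enumeration over 11 patients.** Even-numbered patients can always be called at 83% or better. Odd-numbered patients are 50/50 unless a block of 4 has begun with two alike.

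| Patient | Callable at ≥80% | Certain | Best guess correct |
|---|---|---|---|
| 1 | 0 | 0 | 0.500 |
| 2 | 1 | 0 | 0.833 |
| 3 | 0.167 | 0.167 | 0.583 |
| 4 | 1 | 0.167 | 0.917 |
| 5 | 0.083 | 0.083 | 0.542 |
| 6 | 1 | 0.083 | 0.875 |
| 7 | 0.125 | 0.125 | 0.562 |
| 8 | 1 | 0.125 | 0.896 |
| 9 | 0.104 | 0.104 | 0.552 |
| 10 | 1 | 0.104 | 0.885 |
| 11 | 0.115 | 0.115 | 0.557 |

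The means over the 11 patients are 5.594/11 = 50.9% callable at ≥80%, 1.073/11 = 9.8% certain, and 7.70/11 = 70.0% correct. The other 49.1% stay at 50/50.

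No elaborate calculation is needed on site. Naming whichever arm is behind at the centre is possible for 51% of allocations and is right 89% of the time (76% under blocks of 4, 6 and 8).

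**Sensitivity of the share callable at ≥80%.**
- Centre size, equal mixing: 54.7% for 8 patients, 52.1% for 15, 55.4% for 66.
- Mix, 11 patients: 49.4% if two-thirds of blocks are of size 2; 38.7% if one-third are. In the latter case patient 2 is called at 1/3 + 2/3 × 2/3 = 77.8%, and 52.1% of allocations are callable at ≥75%.

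**Comparison with randomly varying blocks of 4, 6 and 8 (11 per centre, equal mixing, same observer).**

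| Measure | 2/4 | 4/6/8 |
|---|---|---|
| Callable at ≥60% | 50.9% | 59.1% |
| Callable at ≥70% | 50.9% | 46.6% |
| Callable at ≥75% | 50.9% | 36.6% |
| Callable at ≥80% | 50.9% | 16.0% |
| Callable at ≥85% | 38.4% | 10.4% |
| Certain | 9.8% | 2.4% |
| Mean correct guesses | 70.0% | 65.4% |

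Mean absolute imbalance over six centres of 11, by simulation, is about 1.9 patients for 2/4 and 2.1–2.3 for 4/6/8.

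**The case against.** A reader might infer that concealment is defeated outright. The documents do not support that: REDCap keeps the list hidden, about half of the allocations stay at 50/50 and about one in ten is certain.

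A reader might also take the 51% as a property of the protocol. It depends on equal mixing, which is not stated, and on staff who keep track. With one-third blocks of 2 it falls to 38.7%.

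The contrast of 51% with 16% depends on the 80% threshold. At 70% the two schemes are close, and at 60% the larger blocks do worse. On the measure without a threshold, mean correct guessing, larger blocks gain less than 5 points (70.0% to 65.4%). All of this stands, and it is why the benefit is described as a cut in high-certainty calls.

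The route to bias is also narrower than it may look. The protocol does not say that the physiotherapist recruits. Consent precedes randomisation, so any steering must come earlier. Several exclusions are measured on imaging, and the optional crossover lessens the incentive to steer. Small blocks have a stated purpose, balance, which matters with about 11 patients per centre. These points reduce the risk but do not remove it. Examiners are unblinded, so recruiters can learn past allocations. Some criteria remain judgement calls. The balance bought by blocks of 2 is a fraction of one patient overall. Baseline adjustment covers only what is measured.

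**Conclusion.** The point holds as a weakness of design. With published blocks of 2 and 4 within each centre of an open trial, an informed observer can call about 51% of allocations with at least 80% certainty (about 39–55% across plausible mixes and centre sizes). About 10% are certain, and mean correct guessing is 70% against 50% under simple randomisation. This rests on 11 patients per centre, equal mixing, known sizes and tracked allocations.

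The result measures opportunity for selective enrolment or timing. It does not show that steering will occur, and no effect on the WOSI difference can be derived from the documents. The sample size is not affected. The change should be made because it costs little and closes an avoidable gap.

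**What to change.** In section 6.2.1, remove blocks of 2 and use randomly varying larger blocks within centre, for example 4, 6 and 8, for the part of each list not yet used. State in the protocol only that block sizes vary at random and are not disclosed to sites. Keep the sizes and their proportions in a restricted randomisation file held by the statistician. Withholding the sizes is a necessary half of the change, because larger blocks alone lower mean guessing by less than 5 points; its own contribution is not quantified here.

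The cost is an amendment to one sentence, regeneration of the unused lists, and a mean overall imbalance of about 2.1–2.3 instead of 1.9 patients. Imbalance within a single centre can be somewhat larger. Sites that already hold the protocol know the old sizes, so the new ones must not be circulated with the amendment.
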